15.2 DERIVED EFFICACY AND SAFETY VARIABLES

The total score of each variable including MADRS, [REDACTED] at a particular visit will be calculated using $(\text{sum of nonmissing items}) \times (\text{total number of items}) / (\text{number of nonmissing items})$ only if the number of missing items is less than the specified number for each variable. Otherwise, the total score will be set to missing.

15.3 REPEATED OR UNSCHEDULED ASSESSMENTS OF SAFETY PARAMETERS

If a patient has repeated assessments before the start of DB treatment, the results from the final nonmissing assessment made before the start of the DB IP will be used as baseline. If end-of-study assessments are repeated or if unscheduled visits occur, the last nonmissing postbaseline assessment will be used as the end-of-study assessment for generating summary statistics. However, all postbaseline assessments will be used for PCS value determinations, and all assessments will be presented in the data listings.

15.4 MISSING SEVERITY ASSESSMENT FOR ADVERSE EVENTS

If severity is missing for an AE that started before the date of the first dose of DB IP, an intensity of mild will be assigned. If severity is missing for an AE that started on or after the date of the first dose of DB IP, an intensity of severe will be assigned. The imputed values for severity assessment will be used for the incidence summary; the values will be shown as missing in the data listings.

15.5 MISSING CAUSAL RELATIONSHIP TO INVESTIGATIONAL PRODUCT FOR ADVERSE EVENTS

If the causal relationship to the IP is missing for an AE that started on or after the date of the first dose of DB IP, a causality of yes will be assigned. The imputed values for causal relationship to randomized treatment will be used for the incidence summary; the values will be shown as missing in the data listings.

15.6 MISSING DATE INFORMATION FOR ADVERSE EVENTS

The following imputation rules only apply to cases in which the start date for an AE is incomplete (ie, partly missing). If the patient did not receive any randomized dosing during the study, then the date of first dose of DB IP will be utilized for the purpose of imputation.

Missing month and day

- If the year of the incomplete start date is the same as the year of the first dose of randomized IP, the month and day of the first dose of randomized IP will be assigned to the missing fields.
- If the year of the incomplete start date is before the year of the first dose of randomized IP, *31 Dec* will be assigned to the missing fields.
- If the year of the incomplete start date is after the year of the first dose of randomized IP, *01 Jan* will be assigned to the missing fields.

Missing month only

- If only the month is missing, the day will be treated as missing and both the month and the day will be replaced according to the above procedure.

Missing day only

- If the month and year of the incomplete start date are the same as the month and year of the first dose of randomized IP, the day of the first dose of randomized IP will be assigned to the missing day.
- If either the year of the incomplete start date is before the year of the date of the first dose of randomized IP or if both years are the same but the month of the incomplete start date is before the month of the date of the first dose of randomized IP, the last day of the month will be assigned to the missing day.
- If either the year of the incomplete start date is after the year of the date of the first dose of randomized IP or if both years are the same but the month of the incomplete start date is after the month of the date of the first dose of randomized IP, the first day of the month will be assigned to the missing day.

If the stop date is complete and the imputed start date as above is after the stop date, the start date will be imputed by the stop date.

If the start date is completely missing and the stop date is complete, the following algorithm will be used to impute the start date:

- If the stop date is after the date of the first dose of randomized IP, the date of the first dose of randomized IP will be assigned to the missing start date.
- If the stop date is before the date of the first dose of randomized IP, the stop date will be assigned to the missing start date.

15.7

MISSING DATE INFORMATION FOR PRIOR OR CONCOMITANT MEDICATIONS

For prior or concomitant medications, including background ADT, incomplete (ie, partially missing) start dates and/or stop dates will be imputed. When the start date and the stop date are both incomplete for a patient, the start date will be imputed first. If the stop date is complete and the imputed start date is after the stop date, the start date will be imputed using the stop date. If the imputed stop date is before the start date (imputed or nonimputed start date), the start date will be the imputed stop date. If the patient did not receive any randomized dosing during the study, then the date of first dose of DB IP will be utilized for the purpose of imputation.

15.7.1

Incomplete Start Date

The following rules will be applied to impute the missing numeric fields for an incomplete prior or concomitant medication start date.

Missing month and day

- If the year of the incomplete start date is the same as the year of the first dose of randomized IP, the month and day of the first dose of randomized IP will be assigned to the missing fields.
- If the year of the incomplete start date is before the year of the first dose of randomized IP, *31 Dec* will be assigned to the missing fields.
- If the year of the incomplete start date is after the year of the first dose of randomized IP, *01 Jan* will be assigned to the missing fields.

Missing month only

- If only the month is missing, the day will be treated as missing and both the month and the day will be replaced according to the above procedure.

Missing day only

- If the month and year of the incomplete start date are the same as the month and year of the first dose of randomized IP, the day of the first dose of randomized IP will be assigned to the missing day.
- If either the year of the incomplete start date is before the year of the date of the first dose of randomized IP or if both years are the same but the month of the incomplete start date is before the month of the date of the first dose of randomized IP, the last day of the month will be assigned to the missing day.
- If either the year of the incomplete start date is after the year of the date of the first dose of randomized IP or if both years are the same but the month of the incomplete start date is after the month of the date of the first dose of randomized IP, the first day of the month will be assigned to the missing day.

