6.1 PROTOCOL DEVIATIONS

Protocol deviations will be defined in Protocol Deviation Requirement Specification, including the classification of significance vs. non-significance. The number and percentage of patients with significant protocol deviations will be summarized by treatment group for the Enrolled Population. A listing of all significant protocol deviations will be provided.

7.0

DEMOGRAPHICS AND OTHER BASELINE CHARACTERISTICS

Demographic parameters and other baseline characteristics (eg, age, race, ethnicity, sex, weight, height, body mass index) will be summarized for all patients combined using the Enrolled Population, mITT Population, placebo responders of mITT Population, and placebo non-responders of mITT Population. An analogous analysis will be performed for baseline efficacy assessments.

Medical and surgical history, psychiatric history, previous treatment with psychotropic medication, and nondrug psychiatric treatment will be summarized by treatment group for the Safety Population.

The *World Health Organization (WHO) Drug Dictionary Enhanced* will be used to classify prior and concomitant medications by therapeutic class. *Prior medication* is defined as any medication taken before the date of the first dose of DB IP during the placebo lead-in period. *Concomitant medication* is defined as any medication taken on or after the date of the first dose of DB IP which is during the placebo lead-in period. If a medication started prior to the first dose of DB IP and continued into the placebo lead-in period, then this medication will be included in the analysis of prior and concomitant medications separately.

The number and percentage of patients with prior and concomitant medication use will be summarized by treatment group and Anatomical Therapeutic Chemical code for the Safety Population.

Multiple medications used by a patient in the same category will be counted only once in the summary tables. Concomitant medications started after the last visit of the randomized treatment period will not be summarized but will be included in the data listings.

Prior ADT treatment in the current episode, as recorded on ATRQ, will be summarized by frequency counts and percentages for patients who took each ADT in adequate dose and duration, total number of ADT taken at adequate dose and duration (ie., 1, 2, 3 or >3), and percentage of improvement reported (ie., < 25%, 25% to 49%, 50% to 75%, or >75%).

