15.7.2 Incomplete Stop Date

The following rules will be applied to impute the missing numeric fields for an incomplete prior or concomitant medication stop date. If the imputed stop date is before the start date (imputed or nonimputed start date), the imputed stop date will be equal to the start date.

Missing month and day

- If the year of the incomplete stop date is the same as the year of the last dose of randomized IP, the month and day of the last dose of randomized IP will be assigned to the missing fields.
- If the year of the incomplete stop date is before the year of the last dose of randomized IP, *31 Dec* will be assigned to the missing fields.

[figure not shown]
- If the year of the incomplete stop date is after the year of the last dose of randomized IP, 01 Jan will be assigned to the missing fields.

Missing month only

- If only the month is missing, the day will be treated as missing and both the month and the day will be replaced according to the above procedure.

Missing day only

- If the month and year of the incomplete stop date are the same as the month and year of the last dose of randomized IP, the day of the last dose of randomized IP will be assigned to the missing day.
- If either the year of the incomplete stop date is before the year of the date of the last dose of randomized IP or if both years are the same but the month of the incomplete stop date is before the month of the date of the last dose of randomized IP, the last day of the month will be assigned to the missing day.
- If either the year of the incomplete stop date is after the year of the date of the last dose of randomized IP or if both years are the same but the month of the incomplete stop date is after the month of the date of the last dose of randomized IP, the first day of the month will be assigned to the missing day.

[figure not shown]

RESTR

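### SAP 15.7 and 15.7.2 give opposite corrections when an imputed medication stop date falls before the start date

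*SAP*

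**What the plan says.** SAP 15.7 opens with general rules for incomplete medication dates, background antidepressant therapy (ADT) included. When both dates are incomplete, the start is imputed first. It then says that if the stop, once imputed, precedes the start (a parenthesis covers imputed and nonimputed starts alike), "the start date will be the imputed stop date".

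SAP 15.7.2, on incomplete stop dates, repeats that condition, including the parenthesis covering imputed and nonimputed starts, but concludes that "the imputed stop date will be equal to the start date".

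Three other rules determine what follows.

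- **Stop imputation (SAP 15.7.2).** If only the day is missing and the month and year match the last randomized dose, "the day of the last dose of randomized IP will be assigned to the missing day". If month and day are missing and the year matches, "the month and day of the last dose of randomized IP will be assigned to the missing fields". An earlier month or year takes its last day, and a later one its first day.
- **Start imputation (SAP 15.7.1).** If month and day are missing and the year matches the first randomized dose, "the month and day of the first dose of randomized IP will be assigned to the missing fields".
- **Tabulation (SAP 7.0).** "Concomitant medications started after the last visit of the randomized treatment period will not be summarized but will be included in the data listings".

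**The concern.** The two sentences share a trigger and change opposite dates. Once either is applied, start and stop are equal and the other no longer triggers, so whichever is programmed first decides the result. The SAP's only ordering statement, that the start is imputed before the stop, does not settle which date gives way.

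The 15.7 sentence also breaks with the SAP's practice elsewhere. In the sentence just before it, and in SAP 15.6 for adverse events, an imputed start yields to a complete stop. Here a fully recorded start can yield to an imputed stop. Since SAP 7.0 uses the start date to separate summarized drugs from those only listed, a drug begun after the last randomized-period visit could be tabulated as if begun during treatment.

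**Working it through.** The plan states no figure to reproduce. The check applies both rules to the same records.

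**Inputs.** The rules are those set out above. SAP Table 15.1-2 targets Day 21 at 7 days after the second randomized dose, so the last visit is taken as last dose + 7 days. The calendar dates are assumptions: first randomized dose 01 Jun 2018, last dose 08 Jun 2018, last visit 08 Jun + 7 = 15 Jun 2018. Case 5 uses last dose 27 Dec 2018 and last visit 03 Jan 2019.

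**Rules.** If imputed stop < start, then 15.7 sets start = imputed stop and 15.7.2 sets stop = start. A concomitant drug is summarized if its final start is on or before the last visit.

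| Case | Start | Stop as collected | Imputed stop | Final start, 15.7 | Final start, 15.7.2 |
|---|---|---|---|---|---|
| 1 | 20 Jun 2018, recorded | Jun 2018 | 08 Jun | 08 Jun, summarized | 20 Jun, listed only |
| 2 | 05 Jul 2018, recorded | 2018 | 08 Jun | 08 Jun, summarized | 05 Jul, listed only |
| 3 | 12 Jun 2018, recorded | Jun 2018 | 08 Jun | 08 Jun, summarized | 12 Jun, summarized |
| 4 | 05 Jul 2018, recorded | Jul 2018 | 01 Jul | 01 Jul, listed only | 05 Jul, listed only |
| 5 | 10 Jan 2019, recorded | 2019 | 01 Jan 2019 | 01 Jan, summarized | 10 Jan, listed only |
| 6 | 2018 only, imputed 01 Jun | Mar 2018 | 31 Mar | 31 Mar, prior | 01 Jun, concomitant |

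Cases 1, 2 and 5 change the tabulation. Cases 3 and 4 change only the dates shown.

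**When a recorded start can trigger the rule.** Take a recorded start and a true stop no earlier than it.

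- Stop month or year before that of the last dose: the imputed stop is the end of the period, so it cannot precede the start. No trigger.
- Same month or year as the last dose: the imputed stop is the last-dose date. It triggers only if the start is after the last dose.
- Later month or year: the imputed stop is the first day of that period, already after the last dose. It triggers only if the start is later still.

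The start must therefore follow the last randomized dose, and the date that replaces it is the last-dose date or later. SAP 7.0 counts a drug as concomitant if taken on or after the first double-blind dose, so it is concomitant under either rule.

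**Case 6.** With a 7-day lead-in, the first double-blind dose is 01 Jun − 7 days = 25 May. A stop in March makes the drug purely prior. The 15.7 rule gives 31 Mar, which agrees with the recorded month. The 15.7.2 rule moves the stop to 01 Jun, contradicts the recorded month and makes the drug concomitant. Neither sentence is right in every case.

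**The case against.** The strongest reply is that little depends on this. The affected output is a descriptive table, and the drug appears in the listings either way. The trigger needs a complete start, an incomplete stop and particular timing. An antidepressant begun in follow-up and still being taken has no partial stop date to impute. Follow-up lasts one week and applies to patients who do not enter RAP-MD-04 (Protocol 9.1). All of this stands, and it limits the point to a minor one.

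Three stronger readings are tempting, and the documents do not support them.

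- A reader might infer that the 15.7 rule can switch a drug between prior and concomitant. For a recorded start and consistent data it cannot, as shown above.
- A reader might infer, because SAP 15.7 names background ADT, that ADT records are at risk. Protocol 9.4.1 has ADT in place at screening and held constant through Visit 11 or early termination, so its recorded start precedes the last dose and cannot trigger the rule. SAP 8.2 and 8.3 compute ADT exposure and compliance from dose amounts, not from these imputed dates.
- A reader might infer that new antidepressant treatment during the double-blind period would be materially misreported. Protocol 9.4.13 requires patients who start a new treatment to be discontinued, and Protocol 9.3.3 has the reason recorded on the study termination page. The medication table is not the only record.

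It could also be said that 15.7.2, as the more specific section, should prevail. The SAP does not say so, and case 6 shows that this would not always give the right answer.

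**Conclusion.** The contradiction is in the current SAP text and needs no assumption to establish. The two sentences cannot both be applied, and the 15.7 sentence permits an imputed value to overwrite a recorded start.

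The consequence is narrow. A drug recorded as started after the last randomized-period visit may be summarized instead of only listed, provided that its stop date is partial and the imputed stop falls on or before that visit. The worked cases assume a last visit 7 days after the last dose; a different gap moves the boundary but not the mechanism. The documents do not give the number of partial stop dates, so the count of affected records could be zero or more and cannot be estimated. No efficacy analysis, population or missing-data rule visible in the documents uses these dates, so the MADRS results are unaffected. This is a drafting inconsistency, worth correcting because correction is cheap.

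**What to change.** Replace both sentences with one rule, stated once in SAP 15.7 and cross-referenced from 15.7.2:

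1. Never change a recorded date or a recorded part of a date.
2. If the start is recorded and the imputed stop precedes it, set the imputed stop equal to the start.
3. If the start is imputed and the imputed stop precedes it, adjust the imputed start fields to agree with the recorded part of the stop date. Set the start to the imputed stop where the recorded start fields allow this.
4. State the order of adjustment when both dates are imputed.

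Deleting the 15.7 sentence and keeping 15.7.2 would protect recorded starts but leave the case 6 error. The proviso in item 3 matters too. With the same example dates, a start of Jul 2018 is imputed to 01 Jul (SAP 15.7.1, month after the first dose) and a stop of 2018 to 08 Jun. The start cannot move to June without contradicting its recorded month, so the stop must give way.

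The cost is a short paragraph in the SAP and a matching change to the medication-date program. No new data are needed.

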15.7.2 Incomplete Stop Date

The following rules will be applied to impute the missing numeric fields for an incomplete prior or concomitant medication stop date. If the imputed stop date is before the start date (imputed or nonimputed start date), the imputed stop date will be equal to the start date.

Missing month and day

- If the year of the incomplete stop date is the same as the year of the last dose of randomized IP, the month and day of the last dose of randomized IP will be assigned to the missing fields.
- If the year of the incomplete stop date is before the year of the last dose of randomized IP, *31 Dec* will be assigned to the missing fields.

[figure not shown]
- If the year of the incomplete stop date is after the year of the last dose of randomized IP, 01 Jan will be assigned to the missing fields.

Missing month only

- If only the month is missing, the day will be treated as missing and both the month and the day will be replaced according to the above procedure.

Missing day only

- If the month and year of the incomplete stop date are the same as the month and year of the last dose of randomized IP, the day of the last dose of randomized IP will be assigned to the missing day.
- If either the year of the incomplete stop date is before the year of the date of the last dose of randomized IP or if both years are the same but the month of the incomplete stop date is before the month of the date of the last dose of randomized IP, the last day of the month will be assigned to the missing day.
- If either the year of the incomplete stop date is after the year of the date of the last dose of randomized IP or if both years are the same but the month of the incomplete stop date is after the month of the date of the last dose of randomized IP, the first day of the month will be assigned to the missing day.

[figure not shown]

RESTR

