9.4.10 Prior and Concomitant Therapy

A list of example medications that are allowed and not allowed as concomitant medications for either episodic or chronic use is provided in Appendix III. Medication history (psychotropic medication history during the previous 5 years and all other medications during the past 12 months) will be recorded at Screening (Visit 1) in the eCRF. Thereafter, any changes in concomitant medications or any new medications added will be recorded in the eCRF.

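### SAP 15.7.2 moves stop dates with the month missing to the last randomized dose, so some drugs recorded at Visit 1 as already stopped are tabulated as concomitant

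*SAP*

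**What the plan says.** **Month and day missing (SAP 15.7.2).** The condition is "If the year of the incomplete stop date is the same as the year of the last dose of randomized IP", and the consequence is that "the month and day of the last dose of randomized IP will be assigned to the missing fields". For earlier years ("If the year of the incomplete stop date is before the year of the last dose of randomized IP") the date becomes 31 December of the recorded year.

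**Month only missing (SAP 15.7.2).** "If only the month is missing, the day will be treated as missing", so the same rule applies.

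**Day only missing (SAP 15.7.2).** If the recorded month is the month of the last dose, "the day of the last dose of randomized IP will be assigned to the missing day". If, in the same year, the recorded month "is before the month of the date of the last dose of randomized IP, the last day of the month will be assigned".

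**What is collected (Protocol 9.4.10).** At Visit 1 the site records "psychotropic medication history during the previous 5 years and all other medications during the past 12 months". Later changes are recorded as they arise.

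**How drugs are classed (SAP 7.0).** Concomitant means "any medication taken on or after the date of the first dose of DB IP". The reference date is therefore Day 0, the start of the placebo lead-in. A drug that began earlier and continued past that date is counted as both prior and concomitant. The tables are by treatment group in the Safety Population.

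**The concern.** Assigning a late stop date is a common cautious default when it is unknown whether a drug overlapped treatment. For a drug entered in the Visit 1 history as stopped, it is known: the drug ended by Visit 1, and Visit 1 precedes Day 0. Nothing in 15.7.2 uses that fact, and no upper limit is placed on the imputed date. When the month is missing and the year is that of the last randomized dose, the drug is carried to that dose and enters the concomitant table.

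The by-arm concomitant table is where a reader looks for psychotropics and other possible confounders taken on treatment. Entries the trial's own record shows to be past use make that table less reliable. The history is collected by recall over 12 months or 5 years, so some incomplete stop dates are to be expected.

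**Working it through.** **Inputs.** The imputation rules are in SAP 15.7.2 and the Day 0 cut-off is in SAP 7.0. The dosing indices are in SAP 15.1, where the last randomized dose is Index0 + 7 + 7 = Day 14 with two randomized doses and Day 7 with one. Screening lasts up to 14 days (Protocol 9.1.1). I used 7 and 14 days.

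**Example (assumed dates).** Day 0 is 20 Jun 2017, so the last dose is 4 Jul 2017. With 14-day screening, Visit 1 is 6 Jun 2017. All the drugs below stopped before Visit 1.

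| True stop | Known part | Imputed stop | Class |
|---|---|---|---|
| 10 Feb 2017 | year | 4 Jul 2017 | concomitant |
| 10 Feb 2017 | month, year | 28 Feb 2017 | prior only |
| 2 Jun 2017 | month, year | 30 Jun 2017 | concomitant |
| 1 Sep 2016 | year | 31 Dec 2016 | prior only |

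In the first row the stop lands 28 days after a visit at which the drug was already recorded as stopped.

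**Share of year-only stops affected, 12-month history.** Assume stop dates spread evenly over the 365 days before Visit 1 and Day 0 equally likely on any day of a 365-day year. Let s be the days from Visit 1 to Day 0.

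A year-only stop is classed as concomitant exactly when its year is the year of Day 0. If the last dose is in that year too, the stop moves to the last dose. If the last dose falls in the next January, the stop becomes 31 December, which is still on or after Day 0. A stop in an earlier year becomes a 31 December before Day 0 and stays prior.

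If k days of the year have passed at Day 0, max(0, k − s) of the 365 possible stop days qualify. Averaged over k = 0 to 364:

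share = (364 − s)(365 − s) / (2 × 365²)

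- s = 7: (357 × 358 / 2) / 133,225 = 63,903 / 133,225 = 48.0%
- s = 14: (350 × 351 / 2) / 133,225 = 61,425 / 133,225 = 46.1%

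A date-by-date count applying the rules literally gives the same figures, with one randomized dose or two. With two doses, 44.3% (s = 7) and 42.5% (s = 14) land on the last-dose date itself. The remainder come through 31 December.

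**Five-year history.** The same qualifying days are divided by 5 × 365 = 1,825 possible days.

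- s = 7: 63,903 / (365 × 1,825) = 9.6%
- s = 14: 61,425 / (365 × 1,825) = 9.2%

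**Day only missing, 12-month history.** The date-by-date count gives 2.4% (s = 7) and 1.1% (s = 14) classed as concomitant. The rest stay prior.

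**With the stop date capped at Visit 1.** The imputed stop always precedes Day 0, so the share falls to 0% in every case above. These runs take the start date as known.

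**The case against.** The best defence is that a late default avoids missing real on-treatment use, and that the consequence is small. The first part stands for drugs whose timing is unknown, and the last-dose default should remain for them. It does not cover a drug whose stop was already on record before dosing.

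Three further points stand as limits on size:

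- Edit checks and queries (Protocol 9.6.2) may leave few incomplete dates, and no count is given.
- SAP 7.0 summarizes previous psychotropic treatment separately, and table specifications are in another document. The documents therefore do not settle whether the full 5-year history feeds the concomitant table.
- The eCRF is not among the documents, so whether it flags drugs as stopped at Visit 1 cannot be confirmed.

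A reader might infer that every incompletely dated drug is carried to the last dose. SAP 15.7.2 does not say that: with only the day missing, an earlier month gets its own last day.

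A reader might also extend the point to drugs stopped during screening or washout. Those stops come after Visit 1, so the Visit 1 record does not contradict the imputed date. The next scheduled visit, Visit 2, is the day of the first dose (Protocol 9.4.7.2). A cap there would still give a date that SAP 7.0 counts as concomitant.

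**Conclusion.** The rule is wrong as written for a defined subset: drugs recorded at Visit 1 as already stopped, with the month of stopping missing and the year equal to that of the last randomized dose. All of these are classed as concomitant against the trial's own record. Under evenly spread stop dates they make up most of the 46 to 48% of year-only stops misclassified over 12 months and the 9 to 10% over 5 years; a few more arise through the 31 December rule at the turn of the year. These are shares of incomplete records, not of all medications.

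The point is minor. Only the descriptive prior and concomitant medication tables are touched. The same rule applies to both arms of a blinded trial, so the error is likely to be similar in each. A reader might infer a threat to the efficacy result, but the MADRS model in SAP 9.1 uses none of these dates. Nor do the documents show that the concomitant table is materially distorted, since the frequency of incomplete dates is unknown.

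**What to change.** Add to SAP 15.7.2: *For a drug recorded at Visit 1 as already stopped, the imputed stop date may not be later than the Visit 1 date.* Keep the last-dose default for all other drugs.

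Apply the cap last. If the start date is also incomplete, SAP 15.7.1 can place it at the first randomized dose, after the capped stop. SAP 15.7 then moves the start date, whereas 15.7.2 moves the stop date and would undo the cap. Those two sentences need reconciling in any case, but reconciling them alone would not cure the problem described here.

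The cost is one sentence and a small programming change. The downside is reliance on the eCRF to identify drugs recorded as stopped at Visit 1. If it cannot, the tables should carry a footnote stating the imputation rule and the number of concomitant entries that rest on an imputed stop date.
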